6 SUBJECT DISPOSITION AND BASELINE CHARACTERISTICS

6.1 Subject Enrollment and Disposition

The number of subjects who screened, screen failed, randomly assigned, and completed in the study will be presented for each sequence, TG group (TG values <200 mg/dL or TG values ≥200-499 mg/dL), and overall. The frequency and percentage of subjects who withdraw or discontinue from the study will be summarized for each sequence and overall for all subjects who are randomly assigned to a sequence. The number of subjects included in each analysis population will be presented for each sequence and overall.

A data listing for subject disposition, including study completion status, will be provided. In addition, analysis populations and reasons for exclusion from the analysis populations will be presented in a data listing.

6.2 Protocol Deviations/Violations

A protocol deviation is a minor departure from the protocol that is approved by the Study Director or authorized designee prior to implementation and does not compromise subject safety or the integrity of the data. The site should accurately document the deviation and approval in the source document and complete the protocol deviation/violation electronic case report form (eCRF).

No deviations from the inclusion/exclusion criteria will be allowed prior to randomization in order to enroll a subject into the study.

A protocol violation is a divergence from the Institutional Review Board (IRB)-approved protocol that is not approved by the Study Director or authorized designee prior to implementation. A violation can be classified as major or minor. A major violation compromises the safety of the subject or the integrity of the data collected. A minor violation is a less-significant departure from the protocol that, though not pre-approved, does not compromise the safety of the subject or the integrity of the data collected. The site should accurately document the violation in the source document and complete the protocol deviation/violation eCRF. Violations that could significantly influence subject safety will be reported to the IRB.

Subjects to be excluded from the PP population will be determined prior to locking the study database for the final analysis and the list of exclusions approved by the study statistician and medical monitor. A listing of these subjects, with the reason for exclusion, will also be generated (Listing 16.2.3.1).

Protocol deviations and violations will be presented in a data listing.

6.3 Demographic and Baseline Characteristics

Subject demographics and baseline data (race, ethnicity, sex, age, weight, height, waist circumference, HbA1c, TSH, mean systolic and diastolic blood pressure and heart rate at baseline, PD parameters at baseline, and body mass index [BMI]) will be summarized by sequence, TG group, and overall for the ITT, safety, PD, and PP populations. Disease characteristics of Type 2 diabetes from medical history and lipid drug use, statin drug use, and ezetimibe use from the medication data will be included.

Categorical data will be summarized using the number and percentage of subjects with a particular attribute. The denominators for calculating the percentages will be the number of subjects in each sequence and/or TG group and population with data.

Numerical data will be summarized using descriptive statistics including the mean, median, SD, minimum, maximum, Q1, Q3, and number of subjects.

Demographics will be provided in a data listing by subject. The baseline characteristics of systolic and diastolic blood pressure, heart rate, weight, height, waist circumference, and BMI will be included in the vital signs data listing. The baseline characteristics of HbA1c, TSH, and laboratory parameters will be included in the safety laboratory data listings. The PD parameter baseline values will be provided in the PD parameter listing.

6.4 Medical History

Medical history will be classified into a standardized terminology using the Medical Dictionary for Regulatory Activities (MedDRA Version 22.0 or higher) system organ classifications and preferred terms and will be listed by subject identifier, medical condition reported term, onset date, and ongoing status/resolution date.

6.5 Nicotine Use

Current nicotine use will be collected for each subject. This information will be used for qualifying subjects for enrollment and not listed.

6.6 Other Screening Assessments

The following screening information and variables will be provided in data listings:

- Inclusion criteria met and exclusion criteria not met;
- Physical examination;
- Randomization schedule.

7 PHARMACODYNAMIC ANALYSES

7.1 Pharmacodynamic Data

The pharmacodynamic analyses will be performed on available data from subjects in the PD population and repeated for the ITT and PP populations.

The PD outcome variables will be summarized using descriptive statistics by treatment at baseline, each postdose visit, and end of treatment (if the average) for the results, change from baseline, and percent change from baseline values. The PD outcomes will be presented in a data listing by parameter for each subject with data. Individual and mean values will be presented, as applicable.

7.2 Pharmacodynamic Statistical Analyses

TG response to each treatment will be summarized using geometric means for baseline values and least squares (LS) geometric means for end of treatment and percent change from baseline. Variability in the geometric means and LS geometric means will be reported as 95% confidence intervals (CIs). LS geometric means and 95% CIs for end of treatment will be computed as the back-transformed LS means and 95% CIs obtained from a mixed effects model using the natural log (ln)-transformed end of treatment values as the dependent variable in the model with terms for the ln-transformed baseline as a covariate, and period, sequence, treatment, and TG group as fixed effects and subject nested within sequence as a random effect. The treatments will be compared using a mixed effects model for the PD population for the primary outcome variable using the ln-transformed values of percent change from baseline in TG + scaling factor of 100 (scaling factor used to account for possible negative values) as the dependent variable in the model with terms for the ln-transformed baseline as a covariate, and period, sequence, treatment, and TG group as fixed effects and subject nested within sequence as a random effect. LS geometric means and 95% CIs for percent change from baseline will be computed as the back-transformed, scaled down LS means and 95% CIs for each treatment. Treatment difference as measured by LS mean differences and 95% CIs will be constructed for the ln-scale values, back-transformed, and expressed as the ratio of geometric means. All subjects with available data will be included in the analyses.

The SAS PROC MIXED code is as follows:

```
PROC MIXED DATA=dataset;  
  BY paramn paramcd param;  
  CLASS subjid trtseqp trta aperiodc TG_group;  
  MODEL ln_pchg=ln_base trtseqp trta aperiodc TG_group / ddfm=kenwardroger;  
  RANDOM subjid(trtseqp);  
  ESTIMATE 'MAT9001 vs Vascepa' trta 1 -1 / cl;  
RUN;
```

In the above statements:

- PARAMN, PARAMCD, and PARAM represent each PD outcome in numeric, short, and long parameter variables;

- SUBJID represents the subject identifier for the study;
- TRTSEQP represents the treatment sequence;
- TRTA represents the treatment (MAT9001 or Vascepa);
- APERIODC represents the treatment period (Period 1 or Period 2);
- TG_GROUP represents the stratified group where subjects were stratified into 1 of 2 TG groups (TG values <200 mg/dL or TG values ≥200-499 mg/dL);
- LN_PCHG represents the ln scale of 100+percent change from baseline in TG;
- LN_BASE represents the ln scale baseline values.

Additional covariates may be added to the model, such as gender, age, BMI, and so on, as necessary, to explain the variability in the data.

Similar analyses will be provided for all secondary outcomes, plasma phospholipid levels of omega-3 fatty acids for Days 22 and 29 of each treatment period, and plasma omega-3 fatty acids for Day 22 of each treatment period and also repeated for the ITT and PP populations.

Exploratory analyses of lipids, apolipoproteins, PCSK9, hs-CRP, and plasma, plasma phospholipid, and erythrocyte membrane levels of omega-3 fatty acids will be performed using data from the first treatment period only. As such, the mixed effect models for the ln-transformed values of percent change from baseline + scaling factor of 100 and the ln-transformed end of treatment values will include terms for the ln-transformed baseline as a covariate, and treatment and TG group as fixed effects. Response within each treatment and treatment differences will be summarized as described for the primary outcome.

An exploratory analysis may be included using the same model as previously described with an added interaction term of Treatment-by-TG group and comparisons of treatment tested for each TG group presented.

Assumptions of normality of residuals will be examined for substantial departures from normality. If there are substantial departures from normality after the ln transformation, another transformation may be applied to the data where the rank transformation of the original values will be used for the analysis in place of the ln transformation.

There will be no adjustment for multiplicity, i.e., multiple testing of secondary outcomes.

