1.2 Endpoints

The primary outcome variable is the percent change from baseline to end of treatment in TG. Baseline will be the average of the values obtained during the final two, pre-treatment visits for each treatment period, and end of treatment will be the average of values collected at the treatment visits on Days 22 and 29.

The secondary outcome variables include percent changes from baseline to end of treatment in the following parameters:

- Total cholesterol (Total-C);
- Low-density lipoprotein cholesterol (LDL-C);
- Very low-density lipoprotein cholesterol (VLDL-C);
- High-density lipoprotein cholesterol (HDL-C);
- Non-HDL-C;
- Apolipoprotein (Apo) AI;
- Apo B;
- Apo C3;
- PCSK9;
- hs-CRP;
- Omega-3 fatty acids (EPA, docosahexaenoic acid [DHA], docosapentaenoic acid [DPA], total EPA+DHA+DPA) in plasma.

The exploratory outcome variables include percent changes from baseline to end of treatment, unless otherwise specified, in the following parameters:

- Plasma phospholipid levels of omega-3 fatty acids (EPA, DHA, DPA, total EPA+DHA+DPA) for Days 22 and 29 of each treatment period, expressed as a concentration and a percentage of total fatty acids;
- Omega-3 fatty acids (EPA, DHA, DPA, total EPA+DHA+DPA) in plasma for Day 22 of each treatment period.
- TG, for the first treatment period only;
- Total-C, for the first treatment period only;
- LDL-C, for the first treatment period only;
- VLDL-C, for the first treatment period only;
- HDL-C, for the first treatment period only;

- Non-HDL-C, for the first treatment period only;
- Apo A1, for the first treatment period only;
- Apo B, for the first treatment period only;
- Apo C3, for the first treatment period only;
- PCSK9, for the first treatment period only;
- hs-CRP, for the first treatment period only;
- Omega-3 fatty acids (EPA, docosahexaenoic acid [DHA], docosapentaenoic acid [DPA], total EPA+DHA+DPA) in plasma for Days 22 and 29 of the first treatment period only;
- Plasma phospholipid levels of omega-3 fatty acids (EPA, DHA, DPA, total EPA+DHA+DPA) for Days 22 and 29 of the first treatment period only, expressed as a concentration and a percentage of total fatty acids;
- Erythrocyte membrane levels of omega-3 fatty acids (EPA, DHA, DPA, total EPA+DHA+DPA), expressed as a percentage of total fatty acids, which will be assessed for the first treatment period only at Days 22 and 29;

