3 RANDOMIZATION PROCEDURES

This is an open-label study. Eligible subjects will be randomly assigned using a computer-generated randomization scheme stratified by TG group (TG values <200 mg/dL or TG values \geq 200-499 mg/dL). If a subject meets all inclusion and none of the exclusion criteria, the following steps should occur at visit 4 (Day 1):

1. Site will utilize an Interactive Web Response System to randomize the subject. The randomization number/sequence will be recorded with the subject's source documentation.
2. Site will complete a Master Study Product Log upon dispensement of study product, which is a list of all study product received and dispensed at the site.

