5 ANALYSIS POPULATIONS AND DATASETS

5.1 Definition of Analysis Populations

Statistical analysis and data tabulation will be performed using the following subject populations unless specified otherwise:

- Intention-to-treat (ITT) population;
- Safety population;
- Pharmacodynamic (PD) population;
- Per protocol (PP) population.

The ITT population will include all subjects who are randomized to a treatment sequence.

The safety population will include subjects who are randomized and receive at least one dose of any study treatment. This will be the primary population for safety analyses.

The PD population will include subjects for whom the estimation of PD parameters will be possible for 2 periods. This will be the primary population for PD analyses. PD parameters cannot be estimated accurately for subjects who have been off of study drug for an extended period prior to measurements. The half-life of EPA from Vascepa is approximately 89 hours (Vascepa Prescribing Information, accessed 01Dec20) and that for EPA from MAT9001 administered in the fed state is approximately 27 hours (MAT-001 clinical study report, 07Jul20). Measurements will not be used for PD estimation from samples obtained from subjects who have been off of study drug for 3 days (72 hours) or more.

The PP population will include all subjects who are included in the PD population for whom compliance for both study periods was at least 80%, and for whom no clinically important protocol violations or deviations occurred during the trial. All decisions regarding inclusion in the PP dataset will be made and documented prior to database lock.

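### The TG models use one ln-baseline slope for a within-subject contrast: valid as planned, but a second baseline term would be a cheap and usually small gain in precision

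*SAP*

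**What the plan says.** - SAP 1.2 defines TG baseline separately for each period: "Baseline will be the average of the values obtained during the final two, pre-treatment visits for each treatment period".
- SAP 5.1 makes the PD population primary for these analyses and requires both periods: "The PD population will include subjects for whom the estimation of PD parameters will be possible for 2 periods".
- SAP 7.2 lists the model terms in prose, "with terms for the ln-transformed baseline as a covariate, and period, sequence, treatment, and TG group as fixed effects and subject nested within sequence", the last of these being random, and gives the primary model in code as `"MODEL ln_pchg=ln_base trtseqp trta aperiodc TG_group / ddfm=kenwardroger"`. A companion model is fitted "using the natural log (ln)-transformed end of treatment values as the dependent variable in the model", with the same terms. Each has a single baseline covariate.
- TG group enters as a fixed effect because the allocation is a "computer-generated randomization scheme stratified by TG group" (SAP 3).
- The code runs over outcomes with `"BY paramn paramcd param"`, and SAP 7.2 extends similar models to all secondary outcomes and repeats them for the ITT and PP populations. It also allows further covariates as needed, with gender, age and BMI as examples.

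**The concern.** With complete pairs, the drug comparison rests on within-subject differences. The best adjustment for the difference between a subject's two baselines is the within-subject slope. A random-intercept model with one slope estimates a weighted mix of that slope and the between-subject slope. The two differ whenever part of the difference between a subject's two baselines is visit-to-visit noise: across subjects, high baseline TG goes with high on-treatment TG, while a noisy difference within a subject predicts less. TG group is a between-subject term and absorbs some of this, but a two-level split cannot separate the slopes. What is at stake is the width of the confidence interval for the primary outcome.

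**Working it through.** **1. The plan's sample size.** Inputs from SAP 2.2: difference 10, SD 28 for the between-treatment difference, power 90%; two-sided alpha 0.05 from SAP 4.
- Normal formula: (28 × (1.960 + 1.282) / 10)² = 82.4, so 83.
- Paired t-test: power 0.899 at n = 84 and 0.902 at n = 85. The 85 reproduces.

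**2. The two TG models are one comparison.** ln(100 + % change) = ln 100 + ln(end of treatment) − ln(baseline). With ln baseline as a covariate, only its slope changes, by exactly 1. The treatment contrast is the same in both.

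**3. Cost of the wrong slope.** Let Δx and Δy be a subject's between-period differences in ln baseline and ln end of treatment, b_W the within-subject slope and b_P the pooled slope. Then Var(Δy − b_P Δx) = Var(Δy − b_W Δx) + (b_P − b_W)² Var(Δx). With equal error SD at baseline and end of treatment, the variance ratio is about 1 + (b_P − b_W)² / (1 − b_W²). Taking slopes from simulation B below:
- b_P 0.55, b_W 0: 1 + 0.3025 = 1.30, interval 14% wider.
- b_P 0.66, b_W 0.30: 1 + 0.1296/0.91 = 1.14, 7% wider.
- b_P 0.72, b_W 0.60: 1 + 0.0144/0.64 = 1.02, 1% wider.

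**4. Simulation A.** n = 85, screening limits applied, TG group in both models, 132 cells × 2,000 trials, REML without the Kenward-Roger correction. Here f is the variance of between-period drift in a subject's TG level divided by the error variance of a two-visit mean. Assumed: f; drift persistence 1.0 or 0.7; between-subject SD of ln TG 0.25 or 0.35; response SD 0.10 or 0.25; treatment-by-subject SD 0.10; median TG 215 mg/dL before screening limits. The SD of the ln-ratio difference is 0.31, 0.36 or 0.42, that is 28 points divided by 89, 78 or 67. Those divisors borrow the 11% and 33% reductions in Protocol 3, which come from a very-low-fat-meal study.

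| f | Cells | Variance, SAP model ÷ two-slope model | Extra CI width |
|---|---|---|---|
| 1, 2, 4 | 72 | 0.996–1.098, median 1.011 | 0–4.8%, median 0.6% |
| 0.25, 0.5 | 48 | 1.012–1.185, median 1.054 | 0.6–8.9% |
| 0 | 12 | 1.042–1.257, median 1.097 | 2.1–12.1% |

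Without TG group the f = 0 ratios are 1.075–1.406, so that term already removes 37–55% of the excess. The pooled slope was 0.23–0.84 against a within-subject slope of 0.00–0.79.

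**5. Simulation B.** Same two models under other assumptions: SD of the ln difference 0.28, response SD 0–0.2, correlation of baseline and end-of-treatment error within a period 0–0.6; 18 null cells × 1,500 trials. Variance ratio 1.02–1.41, median 1.10; standard error 1–19% larger, median 4.7%. Of the six cells with zero correlation, five were at 10–19%.

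**6. Validity without carry-over.** Bias of the SAP model was at most 0.003 on the ln scale. Type I error was 3.9–6.2% in A and 4.0–6.3% in B. Model and empirical standard errors agreed within about 6%.

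**7. The carry-over condition.** SAP 5.1: "The half-life of EPA from Vascepa is approximately 89 hours".
- Visit 7 at least 28 days after visit 6 (general design text, Protocol 5): 2^(−672/89) = 0.5% of EPA left.
- The 28 days run to the crossover, with visit 7 seven days earlier (visit 6 text, Protocol 5): visit 7 can fall at 21 days, and 2^(−504/89) = 2.0% is left.
- If the residual TG effect is proportional (assumption), the baseline shift is at most 0.0197 × |ln 0.89| = 0.0023, and type I error does not change noticeably.
- Stress test, 0.05 ln shift in the Period 2 baseline only: type I error is 4.9–8.8% (SAP model) against 4.7–7.9% (two slopes) in A, and 9–10% against 5–6% in B. Both models rest on the condition.

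**8. What the gain is worth.** If 28 is the SD under the SAP model, variance ratios of 1.05, 1.10, 1.20 and 1.41 raise power at n = 85 from 0.902 to 0.915, 0.927, 0.946 and 0.972.

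**The case against.** The strongest reply is that nothing is wrong. A single baseline covariate with a random subject effect is a legitimate crossover analysis, TG group already recovers part of the loss, and SAP 7.2 leaves room for more covariates. With f of 1 or more the median gain is 0.6% in interval width, so declining the change would be defensible. All of that stands, except that the open covariate clause does not supply the term: it names none that would separate the slopes and leaves its use to discretion. Under SAP 4, an unplanned analysis designed after the SAP is final counts as post hoc.

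It can also be objected that the mean baseline adjusts Period 1 outcomes for a value measured after Period 1 treatment. That is so. Without differential carry-over it does no harm to the treatment contrast, but it is a reason to state the assumption and to keep the term out of the first-period-only models.

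A reader might infer that the pooled slope biases the comparison or inflates type I error, or that 85 subjects are too few. Steps 1 and 6 show neither. Nor is 12% or 19% a ceiling: each is the edge of a grid of assumed values.

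**Conclusion.** The point holds as an efficiency suggestion, not as a defect. The slope is pooled, and the adjustment of the TG contrast is somewhat less precise than the same data allow. The likely loss is 0–5% of interval width with material between-period drift and roughly 2–19% with little. Where the trial falls depends on drift, response variation and error correlation, none of which the documents give. Validity rests on no differential carry-over into the Period 2 baseline. The washout and half-lives make a material shift unlikely, although the two counts of the washout in Protocol 5 differ and must be reconciled. The calculations cover TG only; the gain for other outcomes, such as those with single Day 1 and Day 29 values, is untested. Confidence is medium.

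**What to change.** Before database lock, pre-specify the subject's mean ln baseline over both periods as a second covariate in both two-period TG models, for the PD analysis and its ITT and PP repeats:

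`MODEL ln_pchg=ln_base ln_base_mean trtseqp trta aperiodc TG_group / ddfm=kenwardroger;`

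Leave the RANDOM and ESTIMATE statements as they are, and put the same term in the ln end-of-treatment model. In addition:
- Leave the term out of the first-period-only models.
- For a subject with only one period's baseline, use the mean of the available baselines. Where the Period 1 value serves both periods (SAP Definitions), the mean equals that value.
- If TG is imputed for ITT (the list in SAP 5.2 does not name it), derive the mean within each imputed dataset.
- If the rank fallback in SAP 7.2 is used, derive the mean from the same transformed baselines.
- State the assumption of no differential carry-over.

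Cost: a SAP amendment, one derived variable, one between-subject degree of freedom, and about 1% more variance where the two slopes coincide. TG would need its own PROC MIXED call and would differ from the run for the other outcomes, unless the term is added there too. Both TG models must change together. If only one does, their treatment ratios disagree: in simulation A the 95th percentile of the gap was 0.5–3.1% across cells.

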#### **9.1.9 Fasting omega-3 fatty acids**

Blood samples for fasting plasma and plasma phospholipid omega-3 fatty acids will be collected at treatment 1 visits 4, 5 and 6 (days 1, 22 and 29) and treatment 2 visits 8, 9 and 10 (days 1, 22 and 29). Fasting plasma levels of EPA, DHA, DPA and total omega-3 fatty acids will be assessed. Fatty acids from RBC's will be analyzed from samples collected during treatment 1 only (visits 4, 5, and 6).

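### The exploratory first-period-only analyses default to a population that requires usable data from both periods

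*SAP*

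**What the plan says.** **Populations.** SAP 5.1 states: "The PD population will include subjects for whom the estimation of PD parameters will be possible for 2 periods". It adds: "This will be the primary population for PD analyses". The PP population is a subset of it and further requires at least 80% compliance in both periods and no clinically important deviation during the trial. The ITT population has no such condition: "The ITT population will include all subjects who are randomized to a treatment sequence".

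**Where they apply.** SAP 7.1 gives the general rule: "The pharmacodynamic analyses will be performed on available data from subjects in the PD population and repeated for the ITT and PP populations". SAP 5.2 provides multiple imputation for the ITT analyses and none for the PD or PP analyses.

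**First-period analyses.** SAP 1.2 lists first-period-only versions of TG, the other lipids, the apolipoproteins, PCSK9, hs-CRP and the plasma and phospholipid omega-3 outcomes. It also lists erythrocyte membrane omega-3, which exists for Period 1 only because red-cell fatty acids are measured at visits 4, 5 and 6 alone (Protocol 9.1.9, SAP 2.3). SAP 7.2 takes up this set ("levels of omega-3 fatty acids will be performed using data from the first treatment period only") and specifies models that "will include terms for the ln-transformed baseline as a covariate, and treatment and TG group as fixed effects". The first-period paragraph names no population. The sentence in SAP 7.2 that explicitly repeats analyses in ITT and PP comes before it and covers the two-period analyses.

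**The concern.** With no period, sequence or subject term, the first-period model is a parallel-group comparison of the two products as first received. It needs nothing after visit 6. Its attraction in a crossover is that the groups are those formed by randomisation and no earlier study product can carry over into the data.

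The two-period condition weakens the first of these advantages. Whether a subject yields usable Period 2 data is settled after randomisation and after the Period 1 response. In Period 2 each sequence takes the other product, so the MAT9001-first group would be filtered by events on Vascepa and the Vascepa-first group by events on MAT9001. Loss during washout could also depend on the product taken first. What is at stake is some precision and the full protection of randomisation in the lead version of these analyses.

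**Working it through.** **Step 1: trace one subject through the definitions.** Take a subject who completes visits 4, 5 and 6 with usable values, then withdraws in washout or has no Period 2 on-treatment sample within the 72-hour rule of SAP 5.1.

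| Population | Two-period condition? | Subject in the first-period analysis? |
|---|---|---|
| PD (lead) | Yes | No |
| PP | Yes, plus compliance in both periods | No |
| ITT (repeat under SAP 7.1) | No | Yes, with observed Period 1 values |

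A missing Period 2 baseline alone need not exclude the subject, because the SAP's definition of baseline allows the Period 1 value to stand in. The exclusion turns on Period 2 on-treatment values.

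The SAP 7.2 statement that all subjects with available data are included does not lift the condition. It belongs to the two-period TG models, and SAP 7.1 limits available data to subjects in the PD population.

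**Step 2: reproduce the plan's sample size (SAP 2.2).** Inputs: difference 10, SD 28 for the within-subject treatment difference, two-sided alpha 0.05 (SAP 4), power 90%.

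- n = [28 × (1.960 + 1.282) / 10]² = 82.4, so 83. The paired t calculation gives 90.2% power at n = 85, so the stated 85 reproduces.
- Attrition allowance: 100 − 85 = 15 subjects, and 85 / (1 − 0.15) = 100.

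**Step 3: bound the loss of precision.** If all 100 subjects have usable Period 1 data and N of them meet the two-period condition, the standard error grows by √(100/N).

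| Lost after usable Period 1 data | N | Ratio of standard errors |
|---|---|---|
| 0 | 100 | 1.000 |
| 5 | 95 | 1.026 |
| 10 | 90 | 1.054 |
| 15 | 85 | 1.085 |

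The last row is the ceiling under the plan's allowance. It needs every planned loss to come from a subject who already has usable Period 1 data. Someone lost before giving an on-treatment value has no Period 1 response to exclude.

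**Step 4: translate into power for a 10-point TG difference between groups.** The documents give no between-subject SD, so a range is assumed. The calculation is a two-sample normal approximation on the percentage scale with N/2 per group, although the SAP models a log scale with baseline as a covariate.

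| Assumed SD | Power, N = 85 | Power, N = 100 |
|---|---|---|
| 20 | 63.5% | 70.5% |
| 24 | 48.4% | 54.9% |
| 28 | 37.7% | 43.1% |
| 32 | 30.2% | 34.6% |

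At the ceiling, the restriction costs about 4 to 7 percentage points of power in comparisons that have limited power even with everyone included.

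**The case against.** **The data are kept in ITT.** A reader might infer that valid Period 1 data are thrown away. The documents do not support that. The general rule in SAP 7.1 repeats the pharmacodynamic analyses in the ITT population, which retains every randomised subject. Nor do the subjects at issue depend on imputation: SAP 5.2 imputes missing values only, and these subjects have observed Period 1 data. A reader might also infer that ITT treats off-drug samples differently. The 72-hour rule sits in the PD paragraph of SAP 5.1, but no separate ITT rule is stated. What remains is that the ITT repeat is not the lead version, it adds imputed values for other subjects, and it reaches these analyses only through SAP 7.1.

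**The PD population is inferred here.** This is true of the first-period paragraph, which names none. The inference is nevertheless the ordinary reading of SAP 5.1 with 7.1, and no Period 1 set exists as an alternative.

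**Erythrocyte omega-3.** A reader might conclude that its PD population is empty, since the outcome cannot be estimated in two periods. The population is defined by subject, and the SAP plainly plans this analysis, so that reading cannot be intended. The narrower point stands: inclusion depends on Period 2 data that this outcome never uses.

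**Role and comparability.** The analyses are labelled exploratory, and neither document calls them the carry-over check. Using the same subjects in crossover and first-period tables also makes those tables directly comparable. Both points are fair and limit the importance of the concern. They do not justify selecting on Period 2 in the lead version.

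**Conclusion.** The point holds as a modest design flaw in an exploratory part of the plan. By default, the lead PD version of each first-period analysis, and the PP version, excludes subjects for reasons that arise after Period 1. The comparison is then no longer strictly between the groups as randomised.

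The loss of precision lies between nil and 8.5% on the standard error. This assumes that attrition stays within the planned 15 of 100; the upper end also assumes that all of it follows usable Period 1 data. The documents do not say when losses are expected. They also give no evidence that Period 2 loss depends on product or sequence, so selection bias is possible but its size and direction are unknown. The primary crossover comparison of TG is unaffected.

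**What to change.** In SAP 5.1, define a Period 1 evaluable population: randomised, dosed, with a Period 1 baseline and at least one Period 1 on-treatment value usable under the existing 72-hour rule, irrespective of Period 2. Accepting one value agrees with SAP 5.2, which lets an average rest on a single result. For outcomes read on one day only, the number analysed follows from the values available for that outcome.

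In SAP 7.2, name this as the lead population for all first-period-only analyses, including every erythrocyte membrane outcome. For the PP version of these analyses, apply the compliance and deviation criteria to Period 1 only. State explicitly that the ITT repeat applies to them.

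The cost is SAP wording and one more population flag, with no new data. The number of subjects will differ between the first-period and crossover tables, which a footnote can explain.
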